5.9 Up to day of discharge (but no later than Day 14)

In addition to continuous review of safety and AEs during the second week of hospitalization (up until discharge, as applicable), the following evaluations and assessments will be performed prior to Day 14 or Discharge, whichever is earlier:

- ASIA Impairment Scale scoring. Every attempt will be made to collect scores free of the effects of sedating and/or paralytic drugs.
- Concomitant medications
- Safety labs:
 - Hematology: complete blood count
 - Chemistry: electrolytes (sodium, potassium, chloride, bicarbonate), BUN, creatinine, glucose
- Liver Function Tests: AST, ALT, bilirubin (direct and total), and alkaline phosphatase
- Concomitant procedures and therapies
- Contact information for the subject (home and cellular telephone numbers, email addresses, home addresses, rehabilitation or nursing home information including fax and phone numbers); LAR (home and cellular telephone numbers, email addresses, home addresses); family members (home and cellular telephone numbers, email addresses, home addresses); and personal physician (phone and fax numbers)

5.10 Post-treatment follow-up

- *Post-treatment follow-up: Day 28 (± 7 days)*
 - Review unresolved AEs
 - Record additional AEs
 - ASIA Impairment Scale

- *Post-treatment Follow-up: Day 42 (± 7 days)*
 - Review unresolved AEs
 - Record additional SAEs
 - ASIA Impairment Scale
- *Post-treatment Follow-up: Day 84 (± 14 days)*
 - Review unresolved AEs
 - Record additional SAEs
 - ASIA Impairment Scale
 - Spinal Cord Independence Measure (vIII)
- *Post-treatment Follow-up: Day 182 (± 14 days) and Day 365 (± 30 days)*
 - Review unresolved AEs
 - Record additional SAEs
 - ASIA Impairment Scale
 - Spinal Cord Independence Measure (vIII)

5.11 Study Calendar

Test and Observations	Screening / Enrollment (up to 6 hours prior to treatment)	Day 1	Day 2	Day 3	Day 4	Day 7	Day 14 or D/C	Day 28 (+/- 7 days)	Day 42 (+/- 7 days)	Day 84 (+/- 14 days)	Day 182 (+/- 14 days)	Day 365 (+/- 30 days)
History & Physical	X											

Vital Signs ^a	X												
Consent	X												
Demographic ^b	X												
Operative Data ^f							X						
Length of Stay							X						
Adverse Events ^k	X	X	X	X	X	X	X	X	X	X	X	X	X
Pregnancy Test ^d	X												
SCI (Cervical) ^e	X												
Inclusion/Exclusion	X												
Concomitant Review	X	X	X	X	X	X	X	X					
Procedures	X												
MRI	X		X										
CT	X												
Labs ^c	X	X	X	X	X		X						
ECG(12-lead)	X	X	X	X									
Drug													
Drug Administration ^{i,j}	X	X	X	X									
Serum Biomarkers ^h	X	X		X		X							
Pharmacokinetic ^g	X	X	X	X									
Outcome Measures													
AIS	X	X	X	X	X	X	X	X	X	X	X	X	X
SCIM vIII										X	X	X	

- a. Temperature, blood pressure, pulse, O₂, respiration, BMI, height and weight (can be estimated if patient cannot be measured). Vitals are to be collected at screening (prior to enrolment).
- b. Demographics: age, race, and gender.
- c. Labs: hematology (complete blood count); chemistry (sodium, potassium, chloride, creatinine, electrolytes, bicarbonate, bun); liver function (AST, ALT, bilirubin total, bilirubin direct, and alkaline phosphatase); blood glucose (Blood glucose (BG) monitoring will be hourly (± 30 minutes) for Hours 1-24, every 2 hours (± 30 minutes) for Hours 25-48 and every 4 hours (± 60 minutes) for Hours 49-88. If BG < 70 mg/dL, BG monitoring is required every 15 (± 10 minutes) minutes until BG ≥ 80 for 3 consecutive readings without exogenous bolus glucose supplementation, then hourly (± 30 minutes) for the next 12 hours and every 2 hours (± 30 minutes) thereafter)
- d. Pregnancy test (only complete if woman is of childbearing potential).
- e. SCI (cervical): time, cause, and level of injury.
- f. Optional: only required if patient has surgery.
- g. Blood sampling for PK prior to dosing, at 4-6 hr. (prior to the second dose of glyburide (glyburide), 24±6 hours, 48±6 hours and 60-72 hours. PK samples to be drawn as close as possible to ECGs.
- h. Serum biomarkers: enrollment/baseline, 24 hours, Day 3, and Day 7.
- i. Cannot continue until enrollment liver function test are available and indicate ALT ≤ 3 X upper limit of normal and Bilirubin ≤ 2 X upper limit of normal
- j. Dosing regimen is 12 doses of glyburide; an initial dose of 1.25 mg followed by eleven consecutive doses of 0.625 mg every 6 hours. The total daily dose of glyburide on Day 1, Day 2 and Day 3 will be 3.125 mg, 2.5 mg, and 2.5 mg respectively (see table 2)
- k. AEs/SAEs recorded through Day 28; new SAEs and unresolved AEs recorded through end of study.

6.0 ADVERSE EVENTS

An *adverse event* (AE) is any symptom, sign, illness or experience that develops or worsens in severity during the course of the study. Intercurrent illnesses or injuries should be regarded as adverse events. Abnormal results of diagnostic procedures are considered to be adverse events if the abnormality:

- results in study withdrawal, or
- is associated with a serious adverse event, or
- is associated with clinical signs or symptoms, or
- leads to additional treatment or to further diagnostic tests, or
- is considered by the investigator to be of clinical significance.

For this study, all AE's whether reported, observed, or elicited by direct or indirect questioning will be recorded from the time of study enrollment through study completion. Minimum information required for each AE includes type of event, duration (start and end dates), severity, seriousness, causality to Study Drug, action taken, and outcome.

All unresolved AEs will be followed, whenever possible, until the events are resolved or stabilized, the subject is lost to follow-up, and/or it has been determined that the study treatment or participation in the study is not the cause. At the last scheduled assessment, the investigator should instruct each subject to report any subsequent event(s) that the subject or the subject's personal physician believes might reasonably be related to participation in this study.

Information on AEs should be recorded in the patient record, and also in the appropriate AE page of the REDCap database.

6.1 *Adverse Event Reporting*

Preexisting Condition

A preexisting condition is one that is present at the start of study drug administration. A preexisting condition should be reported as an adverse event if the frequency, severity, or the character of the condition worsens during the study period.

Abnormal Laboratory Values

A clinical laboratory abnormality should be reported as an adverse event if the following conditions are met:

- The laboratory abnormality is not otherwise refuted by a repeat test to confirm the abnormality, and
- The abnormality suggests a disease and/or organ toxicity, and
- The abnormality is of a degree that requires active management; e.g. change of dose, discontinuation of the drug, more frequent follow-up assessments, further diagnostic investigation, etc.

However:

- Electrolyte imbalances that are asymptomatic and not considered clinically significant by the investigator should not be reported as AEs even if they are treated; and
- Table 1 in Section 3.1 defines which blood glucose values should be reported as AEs.

Hospitalization, Prolonged Hospitalization or Surgery

Any AE that results in hospitalization or prolonged hospitalization, according to the judgment of the clinical investigator, should be documented and reported as a Serious Adverse Event (SAE).

Neither the condition, hospitalization, prolonged hospitalization, nor surgery are to be reported as an adverse event in the following circumstances:

- Hospitalization or prolonged hospitalization for diagnostic or elective surgical procedures for a preexisting condition. Surgery should not be reported as an outcome of an adverse event if the purpose of the surgery was elective or diagnostic and the outcome was uneventful.
- Hospitalization or prolonged hospitalization required to allow efficacy measurement for the study.
- Hospitalization or prolonged hospitalization for therapy of the target disease of the study, unless it is a worsening or increase in frequency of hospital admissions as judged by the clinical investigator.

6.2 *Evaluating Adverse Events*

All AEs must be evaluated by the Investigators for severity, seriousness, and relationship to Study Drug.

Adverse Event Severity and Seriousness

All AEs will be evaluated by the Investigators separately for both severity (mild, moderate, severe respectively coded as 1, 2, or 3; see appendix 1) and for seriousness (AE versus SAE).

Relationship to Study Drug

The relationship of the AE to glyburide will be specified by the Investigators as either Unrelated, Possibly/Probably related, and definitely related. When considering the potential relationship of an AE, the Study Investigators' assessment will include consideration of the incidence of complications anticipated in the SCI population in the absence of glyburide administration. For instance, in 485 subjects with acute SCIs recruited into the NACTN database, 1376 total complications were recorded during the initial hospitalization (Table 4) [21].

Table 4: Acute care complications: type, frequency, and incidence

Complication Type	Frequency (%)	Incidence Rate (%)
Pulmonary	348 (25.3)	36.7
Infection	285 (20.7)	33.2
Hematology	213 (15.5)	26.6
Cardiac	178 (12.9)	25.6
GI/GU	115 (8.4)	17.1
Skin	113 (8.2)	16.7
Neuropsychiatric	106 (7.7)	19.2
Death	18 (1.3)	3.7

Specifically, the following events are commonly anticipated in the SCI population in the absence of Study Drug (also see appendix 1):

Version #4

IRB Approval Date:

- Abscess
- Acute Lung Injury and Acute Respiratory Distress Syndrome
- Adjustment disorder/depression
- Autonomic dysreflexia/dysregulation
- Bradycardia
- Acute renal failure
- Anemia
- Cardiac Arrest
- Cholecystitis
- Congestive heart failure/cardiogenic pulmonary edema
- CNS infections
- Coagulopathy
- Cognitive deterioration
- Construct failure
- Deep venous thrombosis
- Depression/Adjustment disorder
- Failure of orthosis
- GI hemorrhage
- Hematuria
- Ileus
- Infectious diarrhea
- Loss of reduction
- Myocardial infarction
- Other dysrhythmia
- Pancreatitis
- Neuropathic pain
- Pulmonary embolus
- Pneumonia
- Progressive neurologic decline (motor and/or sensory)
- Psychosis
- Respiratory failure
- Seizure
- Sepsis

- Shock
- Skin complication (e.g., sacral or operative wound)
- Spinal cord edema and hemorrhage
- Thrombocytopenia
- Urinary Tract Infection
- Wound infection

In this study, AEs will be continually monitored through Day 14 or up until discharge (whichever is earlier). AEs will be further reviewed and additional AEs recorded on Day 28 (± 7 days); AEs will be followed for resolution through the end of the study. Beyond Day 28 through the end of the study, only new SAEs will be recorded.

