1.4 Statistical Considerations

Descriptive statistics will be generated for all variables of interest. Categorical measures will be reported with frequencies, percentages and continuous measures with means and standard deviations.

The primary outcomes of feasibility will be the rate of recruitment and the proportion of patients recruited versus screened.

All adverse events that occur during the initial hospitalization period will be summarized. The frequency of adverse events during this period will be compared to matched NACTN Registry historical controls in a 1:3 ratio (along with corresponding confidence intervals).

Matched tests will be utilized to compare neurologic outcomes and biomarker levels between enrolled subjects receiving oral glyburide and matched historical controls.

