4.4 Study-related management (non-standard of care)

Non-standard-of-care blood work will be obtained at the following time points following the SCI:

- Pharmacokinetic Analysis: Daily, baseline through Day 3
- Biomarkers Levels: Enrollment/Baseline, 24 hours, Day 3, and Day 7

Clinical, imaging, and safety assessments will be performed throughout the study period:

- Patients will be closely monitored clinically for all AEs during the first 28 days of the study. SAEs will be monitored for the entire duration of the study. For the initial hospitalization period, the incidence of AEs will be compared where possible to that of matched controls obtained from the NACTN registry (1:3 ratio with respect to age, co-morbidities, injury level, and injury severity). The 1:3 patient matching will be undertaken by the study statistician.
- Neurological evaluation will be carried out at specific time-points up to one year following SCI to assess for changes in neurological status. The 3, 6, and 12-month ISNCSCI motor/sensory and SCIM vIII scores of the patients will also be compared where possible to that of matched controls from the literature and from the NACTN registry.

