5.4 On-Study: Baseline

These evaluations occur following subject enrollment, prior to the subject receiving glyburide

- Concomitant medications (including all medications taken within 7 days prior to screening)
- Medical procedures (performed since acute SCI)
- Baseline AEs (beginning at the time of enrollment)
- PK sample (serum)
- Biomarker sample (serum)
- CT and MRI studies
 - CT studies will be performed and reviewed prior to enrollment. Standard of care cervical MRI may be initiated prior to start of study drug but this is not a requirement. Study drug will be administered as soon as possible following enrollment irrespective of whether MRI has been performed.

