7.0 STATISTICAL CONSIDERATIONS

Descriptive statistics will be generated for all variables of interest. Categorical measures will be reported with frequencies and percentages and continuous measures with means and standard deviations. The frequency of AEs will be reported (as captured on the modified NACTN form) and, where possible, will be compared to those of the matched controls (along with corresponding confidence intervals). We will match study patients and the historical NACTN cohort data on criteria including: age, co-morbidities, injury level, and injury severity (ASIA A, B or C SCI). Additionally, the number of patients who were otherwise eligible for the study but did not enroll due to lack of infusion within 6 hours will be reported. Secondarily, matched tests will be utilized to compare neurologic outcomes between those receiving glyburide and matched historical controls.

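### Adverse events in the NACTN comparison are counted from enrolment in treated patients but, on a plain reading, from admission in controls

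*Combined protocol and SAP*

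**What the plan says.** Section 3.1 makes the comparison of AE frequency with a matched NACTN cohort part of the primary safety objective. Section 1.4, having named the initial hospital stay as the period, says: "The frequency of adverse events during this period will be compared to matched NACTN Registry historical controls in a 1:3 ratio". Section 4.4 agrees: "For the initial hospitalization period, the incidence of AEs will be compared where possible to that of matched controls obtained from the NACTN registry".

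For treated patients, Section 6.0 says that all AEs "will be recorded from the time of study enrollment through study completion". Section 6.1 adds a second cut, at first dose: "A preexisting condition is one that is present at the start of study drug administration". Such a condition "should be reported as an adverse event if the frequency, severity, or the character of the condition worsens during the study period". Section 5.4, which covers the interval after enrolment and before first dose, lists "Baseline AEs (beginning at the time of enrollment" among the items to collect.

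For the registry, Section 6.2 says that in 485 subjects "1376 total complications were recorded during the initial hospitalization". Section 7.0 matches patients to controls "on criteria including: age, co-morbidities, injury level, and injury severity (ASIA A, B or C SCI". Neither Section 7.0 nor any other section sets a common start of counting or says how the baseline AEs of Section 5.4 enter the comparison.

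**The concern.** The two groups are compared over what is called the same period, but the recording rules open that period at different moments. A treated patient has already been in hospital for some time at enrolment. Respiratory failure, bradycardia or shock (all on the Section 6.2 list of events expected without study drug) that begins in that time and then stays stable or resolves need not be reported as an AE. The same event in a control falls inside the hospital stay.

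There is a second ambiguity inside the treated group. An event that starts after enrolment and is still present at first dose is a baseline AE under Section 5.4 and a pre-existing condition under Section 6.1. With at most 10 treated patients, one classification decision changes a class incidence by 10 points, so the rule should be fixed before the comparison is run.

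At stake is a component of the primary safety objective that Section 2.0 expects to inform phase II/III design. The confidence interval promised in Sections 1.4 and 7.0 reflects sampling error only; it neither reveals nor corrects a difference in counting windows.

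**Working it through.** **1. The windows side by side**

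| Onset of complication | Treated patient | Registry control |
|---|---|---|
| Admission to enrolment, does not worsen later | Not an AE (6.0, 6.1) | Counted, if registry recording starts at admission (6.2) |
| Admission to enrolment, worsens later | AE (6.1) | Counted, same condition |
| Enrolment to first dose, present at first dose, does not worsen | Baseline AE (5.4) or pre-existing (6.1): unclear | Counted |
| After first dose | AE | Counted |

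The first row is a definite mismatch, conditional on the registry start. The third is unresolved.

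**2. The plan's benchmark (Section 6.2, Table 4)**

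The counts 348 + 285 + 213 + 178 + 115 + 113 + 106 + 18 sum to 1376, as stated. Each count divided by 1376 gives the stated share, and 18/485 = 3.7% gives the stated death incidence. The other incidences count patients rather than events and cannot be rebuilt from the event counts. Those used below are 36.7% (pulmonary) and 25.6% (cardiac).

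**3. Length of the gap**

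First dose is due within 8 h of injury (Section 4.1). Section 5.3 cites a riluzole study with injury-to-admission mean 3.0 h and median 2.3 h. Hospital time before first dose is then up to about 8 - 3.0 = 5 h, or 8 - 2.3 = 5.7 h; 8 h is the outer limit. The part that is clearly unrecorded, admission to enrolment, is shorter.

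**4. Size with no drug effect**

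Let p be the control incidence and f the share of affected controls whose only event of that class falls in the gap. Expected treated incidence is p(1 - f), so the shift is -pf. The documents do not give f.

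*Constant event rate, 14-day stay (assumed).* The share of events is 5/336 = 1.5% to 8/336 = 2.4%. Using this for f overstates the loss, because a patient with several events drops out only if all are early. Shift: pulmonary 36.7 × 5/336 = 0.5 to 36.7 × 8/336 = 0.9 points; cardiac 0.4 to 0.6 points.

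*Early clustering (assumed f).*

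| f | Pulmonary, treated vs 36.7% | Cardiac, treated vs 25.6% |
|---|---|---|
| 5% | 34.9% (-1.8) | 24.3% (-1.3) |
| 10% | 33.0% (-3.7) | 23.0% (-2.6) |
| 20% | 29.4% (-7.3) | 20.5% (-5.1) |
| 30% | 25.7% (-11.0) | 17.9% (-7.7) |

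**5. Against precision**

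The 95% half-width is 1.96 × √[q(1 - q)/10 + p(1 - p)/30], with q = p(1 - f), treating the groups as independent and ignoring matching. For f from 0 to 30% it runs from 34.5 to 32.1 points (pulmonary) and from 31.2 to 28.4 points (cardiac). At f = 20% the pulmonary shift equals 10 × 0.073 = 0.7 of a patient among 10.

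**The case against.** The strongest reply has five parts.

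- **Pre-existing conditions are not lost outright.** Section 6.1 brings them back if they worsen, and Section 5.4 collects events from enrolment. This stands: a reader might infer that everything present at first dose is excluded, and the text does not say so. What is left is the stable or resolving event before enrolment, and the unclear status of events between enrolment and first dose.
- **The registry's start is not stated.** The documents speak of the initial hospital stay; that counting begins at admission is an inference. The modified NACTN form is an attachment not included with the text and may carry its own time frame. This also stands, and is why the sponsor has to confirm the start.
- **The net direction is not established.** A reader might conclude that the comparison will make glyburide look safer. The documents do not support that. Treated patients have a broad AE definition with direct questioning (6.0), hourly glucose checks on the first day, telemetry and serial ECGs (5.8), and mandatory AE reporting of confirmed glucose of 55-69 mg/dL (3.1), all of which push the treated count up. Only the window component, taken alone, lowers it.
- **The size is assumed.** No section gives onset times, so early clustering of cardiac and pulmonary events is plausible but undocumented. The constant-rate figure is under 1 point.
- **Nothing formal hangs on it.** The comparison is made where possible, with no test threshold or go/no-go rule. Stopping rules are per patient (6.4), early termination rests on AE review by the principal investigator and the monitoring committee (8.0), and Section 10.0 asks for cautious reading.

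The last two points limit the importance. They do not remove the mismatch: the stated rules give unequal windows, and an opposing ascertainment difference is no reason to leave them so.

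**Conclusion.** The point holds in a limited form. The start of counting is not aligned between treated patients and controls in a primary safety comparison, and Sections 5.4 and 6.1 leave the interval between enrolment and first dose unresolved. Taken alone, the window lowers the treated count; the direction of the whole comparison is unknown.

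The size is under 1 point of pulmonary incidence at a constant rate over an assumed 14-day stay. If 5-20% of affected controls had their only event in the gap, it is about 2-7 points pulmonary and 1-5 cardiac. Either is small against a half-width of about 28-35 points. The conclusion rests on reading the registry's initial hospital stay as starting at admission; the 5-20% range has no source in the documents. This should be fixed because it is cheap and concerns a primary objective, but it does not by itself undermine the pilot.

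**What to change.** In Sections 6.0 and 7.0, for the NACTN comparison only:

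1. Confirm and state when registry complication recording starts.
2. Complete the modified NACTN form for treated patients from that same start (hospital admission, if confirmed) by chart review. Include events with onset before first dose, and flag them.
3. Report AEs counted from first dose separately, as the description of safety on glyburide.
4. Reconcile Sections 5.4 and 6.1, so that an event between enrolment and first dose has one classification and a stated place in the comparison.
5. If the registry holds onset times, a sensitivity analysis may start counting in each control at the injury-to-first-dose time of its matched treated patient, with the treated patient counted from first dose. A fixed start at 8 h in both groups would not serve: 8 h is the latest permitted first dose, so genuine post-dose events in patients dosed earlier would be dropped. If onset times do not exist, state the limitation.

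The cost is a few sentences and a few hours of chart abstraction per patient for at most 10 patients. Section 5.1 already allows screening and baseline information to come from medical records. Treatment is unaffected.

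### Adverse-event collection is stated two ways, and the Day 28 version stops short of the hospital-stay window used for the registry comparison

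*Combined protocol and SAP*

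**What the plan says.** **Collection period.** Section 6.0 states that all AEs will be "recorded from the time of study enrollment through study completion"; Section 1.3 puts completion at about Day 365. Section 6.2 says instead: "Beyond Day 28 through the end of the study, only new SAEs will be recorded". Footnote k of the calendar (Section 5.11) agrees with Section 6.2: "AEs/SAEs recorded through Day 28; new SAEs and unresolved AEs recorded through end of study". Section 4.4 says "Patients will be closely monitored clinically for all AEs during the first 28 days of the study", with SAEs followed for the whole study, and Section 3.1 likewise assesses AEs through Day 28. In Section 5.10 the Day 28 visit (± 7 days) takes additional AEs of any kind. From Day 42 the instruction for new events is "Record additional SAEs".

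**Comparison period.** Section 1.4, referring to the initial hospitalization, says "The frequency of adverse events during this period will be compared to matched NACTN Registry historical controls in a 1:3 ratio". Section 4.4 agrees: "For the initial hospitalization period, the incidence of AEs will be compared where possible to that of matched controls obtained from the NACTN registry". Neither sets a day limit. Section 6.2 describes the registry's own complication counts as covering the initial hospitalization. Sections 3.1 and 7.0 describe the comparison without repeating this window. Section 3.1 adds all-cause and cardiac mortality to it.

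**Hypoglycemia.** Section 3.1 groups AEs into ten systems for the comparison, one of which holds hypoglycemia and other metabolic events. Table 1 makes confirmed glucose values below 70 mg/dL reportable in treated patients (as SAEs below 55 mg/dL), and Section 5.8 sets a glucose testing schedule for them.

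**The concern.** Comparing AE frequency with matched registry controls is part of the primary safety objective, so both groups need the same counting period and similar detection of events.

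With up to ten centers, two incompatible collection rules could yield different data from different sites. If sites follow the Day 28 rule, a treated patient who stays longer stops contributing new non-serious AEs while the comparison period is still running. That would make the treated group look safer than it is. Unequal detection of hypoglycemia would push the other way and make it look less safe. The two effects run in opposite directions, and their net effect is unknown.

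**Working it through.** 1. **Collection rules side by side.** Take a new non-serious AE with onset on Day 40. Section 6.0 requires it to be recorded. Section 6.2 and footnote k exclude it, and the Day 42 visit list does not ask for it. No reading satisfies both.

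2. **Day 28 rule against the comparison window.** Days of hospital stay without collection of new non-serious AEs = max(0, stay − 28). The documents list length of stay as a calendar item but give no expected value, so the stays below are assumptions.

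| Assumed stay (days) | Days not covered | Share of stay |
|---|---|---|
| 14, 21 or 28 | 0 | 0% |
| 35 | 35 − 28 = 7 | 20% |
| 42 | 42 − 28 = 14 | 33% |
| 60 | 60 − 28 = 32 | 53% |
| 90 | 90 − 28 = 62 | 69% |

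 With 10 treated patients, one patient whose only event in a system is missed moves that system's incidence by 1/10 = 10 percentage points. This is the step size, not an estimate of bias.

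3. **Early Day 28 visit.** The window is 28 ± 7, so Days 21 to 35. Section 6.2 ends continual monitoring at Day 14 or discharge, whichever is earlier. After a visit on Day 21, the next scheduled contact asks only for new SAEs. Onsets on Days 22 to 28 (7 days) are inside the stated collection period, but no visit clearly elicits them. This touches the registry comparison only for patients in hospital on those days, which can include someone discharged on, say, Day 27.

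4. **Registry table.** The Table 4 rows give 348 + 285 + 213 + 178 + 115 + 113 + 106 + 18 = 1376, which reproduces the stated total with nothing left over. Three of the ten systems in Section 3.1 have no row there: failure of stabilization, hypoglycemia/metabolic, and other. The table therefore provides no registry figure for hypoglycemia.

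5. **Glucose testing in treated patients** (Section 5.8). Hours 1–24 hourly: 24. Hours 25–48 every 2 hours: 24/2 = 12. Hours 49–88 every 4 hours: 40/4 = 10. Total 24 + 12 + 10 = 46 scheduled readings, before any repeats triggered by low values. No schedule, threshold or reporting rule is described for controls.

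6. **What unequal detection could do (assumed values).** Let the true risk p be equal in both groups, with full detection in treated patients and a fraction d detected in controls. The spurious risk difference is p − p·d. With p = 20% and d = 50%: 2 of 10 against 3 of 30, a difference of 10 points. With d = 25%: 2 of 10 against 1.5 of 30, or 15 points. Over p = 10–30% and d = 25–50% the range is 5 to 22.5 points. With d = 100% it is zero.

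**The case against.** The long-stay loss is conditional. It needs a patient in hospital past Day 28 who has a new non-serious AE. Dosing ends at 72 hours and the stated half-life is about 10 hours, so such events fall more than three weeks after the last dose. AEs that prolong the stay are SAEs and are recorded anyway. This limits what would be lost and how far it bears on drug causation. It does not restore equal windows, because the planned comparison is of AE frequency whatever the cause.

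Collection is defined by calendar day, so an early Day 28 visit need not end the duty to record. That is fair: the gap lies in the visit lists, not in the stated period, and it is a matter of clarification.

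On mortality, a reader might infer that trial deaths to Day 365 will be set against in-hospital registry deaths. The documents do not say so. Section 3.1 puts mortality in the same sentence as the AE comparison, and Sections 1.4 and 4.4 limit the AE comparison to the initial hospitalization. The window for mortality is unstated, not wrong.

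On hypoglycemia, a reader might infer that the registry does not record it, or that it will inflate a pooled AE count. Neither is supported. Table 4 is a published summary, the modified chart in Appendix 1 is not in the available text, the plan specifies no pooled count, and comparison is promised only where it can be made. That qualifier nevertheless does not say which systems are compared, and the ascertainment described is one-sided.

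**Conclusion.** The contradiction between Section 6.0 and the Day 28 provisions is explicit in current text and must be reconciled. It also matters for the analysis: under the Day 28 rule, non-serious AEs in treated patients still in hospital after that day drop out of a comparison that runs to discharge. The size is unknown because no length of stay is given. It is nil if everyone has left by Day 28 and that visit is not held early, and it grows with each longer stay. Deaths and other SAEs are not lost.

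The early-visit gap, the unstated mortality window and the hypoglycemia comparison are smaller points that the same revision should settle. The hypoglycemia point rests on the absence of any described ascertainment in controls and would fall away if the registry proves equivalent. It would be too strong to conclude that the comparison is already biased by a known amount or in a known net direction.

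**What to change.** 1. **One collection period**, worded identically in Sections 3.1, 4.4, 5.10, 6.0 and 6.2 and footnote k: new non-serious AEs through Day 28 or discharge from the initial hospitalization, whichever is later, and new SAEs to study end. If the Day 28 visit was early, ask at Day 42 about AEs with onset through Day 28. This closes the long-stay gap without needing registry event dates. If the Day 28 cut-off is kept instead, end the non-serious comparison in both groups at the earlier of discharge or Day 28, where registry event dates allow.

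2. **One comparison window.** Repeat the initial-hospitalization window in Sections 3.1 and 7.0, state that mortality uses it in both groups, and report later trial deaths separately. Make sure discharge dates after Day 14 are captured, since the calendar places length of stay in a column for Day 14 or discharge.

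3. **Hypoglycemia.** Report it for treated patients only, with exact 95% confidence intervals (0/10: 0 to 30.8%; 1/10: 0.3 to 44.5%; 3/10: 6.7 to 65.2%). Leave it out of the registry comparison and any pooled count unless equivalent registry ascertainment is confirmed.

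**Cost:** wording changes, slightly longer non-serious AE collection for long-stay patients, one conditional question at Day 42, and a check of registry fields (and of event dates if the Day 28 cut-off is kept).
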